1 STUDY OBJECTIVES AND DESIGN

1.1 Study Objectives

PRIMARY OBJECTIVE

The primary objective is to evaluate visual acuity (VA) of the TOTAL30 soft contact lens and the AOHP soft contact lens.

1.2 Study Description

Key components of the study are summarized in Table 1-1.

Table 1–1 Study Description Summary

Study Design	Prospective, randomized,
	bilateral crossover,
	controlled, subject-masked
Study Population	Volunteer subjects aged ≥ 18 years who are any habitual
	spherical soft contact lens wearers, have at least 3 months of
	contact lens wearing experience, and who would be willing to
	wear the study lenses for at least 5 days per week and at least 8
	hours per day.
	Pregnant and breastfeeding women are excluded for this study.
	Target to complete: 32
	Planned to enroll: ~36
Number of Sites	1
	UK
Test Product(s)	TOTAL30 soft contact lenses (TOTAL30)
Commonator Product	ACUVUE OASYS® with HYDRACLEAR PLUS® soft contact
Comparator Product	
D1 1D (; C	lenses (AOHP)
Planned Duration of	Test Product: 28 days
Exposure	Comparator Product: 14 days

[figure not shown]
Visits	Pre-screening
	Visit 1: Screen/Baseline/Dispense Pair 1 [Day 1]
	Visit 2: Follow-up Pair 1/Dispense Pair 2 [AOHP Day 14 (-3/+7
	days); TOTAL30 Day 28 (-3/+7 days)]
	Visit 3: Follow-up Pair 2/Exit [AOHP Day 14 (-3/+7 days);
	TOTAL30 Day 28 (-3/+7 days)]

1.3 Randomization

A member of the Randomization Programming group at Alcon who is not part of the study team will generate the randomized allocation schedule(s) for treatment (lens) sequence assignment. Randomization will be implemented in the Electronic Data Capture (EDC)/randomization integration system.

Subjects will be randomized in a 1:1 ratio to receive treatment in crossover sequence of test product then comparator product or comparator product then test product, respectively.

Sequence	Lens Name
Sequence 1	TOTAL30/AOHP
Sequence 2	AOHP/TOTAL30

1.5 Interim Analysis

There are no plans to conduct an interim analysis and no criteria by which the study would be terminated early based upon statistical determination.

2 ANALYSIS SET

2.1 Safety Analysis Set

Safety analyses will be conducted using the safety analysis set on a treatment-emergent basis. As such, the safety analysis set will include all subjects/eyes exposed to any study lenses evaluated in this study,

For treatment-emergent safety analyses, subjects/eyes will be categorized under the actual study lenses exposed in the corresponding lens sequence.

Adverse events occurring from the time of informed consent but prior to first exposure to the study product will be summarized in subject listings.

3 SUBJECT CHARACTERISTICS AND STUDY CONDUCT SUMMARIES

The following tables will be presented:

- Subject Disposition by Lens Sequence
- Analysis Set by Lens
- Analysis Set by Lens Sequence
- Subject Accounting by Lens Sequence
- Demographics Characteristics by Lens Sequence
- Baseline Characteristics by Lens Sequence

In addition, the following subject listings will be provided:

- Listing of Subjects Excluded from Protocol Defined Analysis Set
- Listing of Lens Sequence Assignment by Investigator
- Listing of Subjects Discontinued from Study

4 EFFECTIVENESS ANALYSIS STRATEGY

This study defines one primary endpoint

will use the Safety Analysis Set.

Continuous variables will be summarized using the number of observations, mean, standard deviation, median, minimum, and maximum. Categorical variables will be summarized with frequencies and percentages from each category.

All data obtained in evaluable participants/eyes will be included in the analysis. No imputation for missing values will be carried out.

4.1 Effectiveness Endpoints

Primary Effectiveness Endpoint

[figure not shown]
The primary endpoint is distance VA with study lenses, collected for each eye in logMAR.

4.2 Effectiveness Hypotheses

Primary Effectiveness

No inferences are to be made on the primary effectiveness endpoint; therefore, no hypotheses are formulated.

4.6 Interim Analysis for Effectiveness

No interim analysis is planned for effectiveness endpoints.

5 SAFETY ANALYSIS STRATEGY

The focus of the safety analysis will be a comprehensive descriptive assessment of occurrence of adverse events as well as the other listed parameters. Therefore, no inferential testing will be done for the safety analysis.

5.1 Safety Endpoints

The safety endpoints are:

- Adverse events (AE)
- Biomicroscopy Findings
 - o Limbal hyperemia
 - o Bulbar hyperemia
 - Corneal staining
 - Conjunctival staining
 - o Palpebral conjunctival observations
 - Corneal epithelial edema
 - Corneal stromal edema
 - o Corneal vascularization
 - o Conjunctival compression/indention
 - o Chemosis
 - Corneal infiltrates

- Other findings
- Device deficiencies

5.2 Safety Hypotheses

There are no formal safety hypotheses in this study. The focus of the safety analysis will be a comprehensive descriptive assessment of safety endpoints listed in Section 5.1.

5.3 Statistical Methods for Safety Analyses

The analysis set for all safety analyses is defined in Section 2.1. Baseline will be defined as the last measurement prior to exposure to study lenses. For biomicroscopy data, baseline will be defined as Visit 1 for pair 1 and Visit 3 for pair 2.

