Randomization		X					
VA w/ study lenses, (OD, OS, logMAR distance)		X (optimization and baseline measurements for both study lens types)	X (lens pair 1)		X (lens pair 2)	X	X
Slit-lamp photo/video of study lenses*		(X)	(X)		(X)	(X)	(X)
Dispense (provide) study lenses		X					(X)

Procedure/ Assessment	Pre-screening	LENS PAIR 1		LENS PAIR 2		Early Exit	USV
		Visit 1 Screen/Baseline/ Dispense Pair 1	Visit 2 Follow-up Pair 1 ^S / Dispense Pair 2	Visit 3 Follow-up Pair 2 ^S /Exit			
		Visit Window ^Ω		Visit Window ^Ω			
		Day 1	AOHP = [Day 14 (-3/+7 days)] TOTAL30 = [Day 28 (-3/+7 days)]	AOHP = [Day 14 (-3/+7 days)] TOTAL30 = [Day 28 (-3/+7 days)]			
Subjective VAS questionnaire		X (baseline measurements for both study lens)	X (lens pair 1)	X (lens pair 2)		X	(X)

AEs		X	X	X	X	X
Device deficiencies		X	X	X	X	X
Exit Form		(X)	(X)	X	X	(X)

(X) Assessment performed as necessary, eg, decrease of VA by 2 lines or more with investigational product (IP)

USV = Unscheduled Visit

* Source only

^S Subjects are required to wear the study lenses at least 6 hrs on the day of follow-up visits prior to the visit. Follow-up visit time to be within ±2 hours of baseline visit time.

^Ω Visit 2 and 3 visit window and exposure period is dependent on the randomized treatment sequence. AOHP exposure period is to be 14 days (-3/+7 days) and TOTAL30 exposure period is to be 28 days (-3/+7 days)

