10 STUDY PROCEDURES AND ASSESSMENTS

Visit #	Visit Type	Visit Day	Visit Window
Visit 1	Screen/Baseline/Dispense Pair 1	Day 1	N/A
Visit 2	Follow-up Pair 1 (Dispense Pair 2) AOHP: Day 14 TOTAL30: Day 28	Day 14 Day 28	Days 11-21 Days 25-35
Visit 3	Follow-up Pair 2/Exit AOHP: Day 14 TOTAL30: Day 28	Day 14 Day 28	Days 11-21 Days 25-35

Unscheduled Visits and Early Termination Visits are allowed, if necessary.

Study lenses will be provided to the subjects to take home for daily wear during the course of the trial.

Study randomization will occur at Visit 1 with assigned lenses provided to take home at Visit 1 and Visit 2. Study contact lens fitting will occur at Visit 1 for both study lenses. If a subject cannot be successfully fit (either study lens) according to the study lens fitting guides as determined by the investigator, they will be required to exit from the study.

Lubrication/rewetting drops will not be permitted during this study.

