12.6 Safety Analyses

The safety endpoints are:

- AEs
- Biomicroscopy findings
- Device deficiencies

There are no safety hypotheses planned in this study. The focus of the safety analysis will be a comprehensive descriptive assessment of occurrence of adverse events as well as the other listed parameters.

All AEs occurring from the time a subject signs informed consent to study exit will be accounted for in the reporting. Safety analyses will be conducted using the safety analysis set on a treatment-emergent basis. Descriptive summaries (counts and percentages) for ocular and nonocular AEs will be presented by Medical Dictionary for Regulatory Activities Preferred Terms. AEs leading to study discontinuation, significant non-serious AEs, and SAEs will be identified. Individual subject listings will be provided, as necessary.

Individual subject listings will be provided for AEs that occur after signing informed consent but prior to exposure to IP.

Each biomicroscopy parameter will be tabulated by its grade. For each biomicroscopy parameter, counts and percentages of eyes that experience an increase of ≥ 2 grades from baseline (last assessment prior to study lens exposure for each period) to any subsequent visit within the same period will be presented. A supportive listing will be generated which will include all biomicroscopy data from all visits within the same period for those eyes experiencing the increase.

Two listings for device deficiencies, prior to exposure of study contact lenses and treatment-emergent, will be provided. Additionally, each device deficiency category will be tabulated.

No inferential testing will be done for safety analysis.

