5.3.2 Biomicroscopy Findings/Slit Lamp Examination

The following tables and supportive listings will be provided:

- Summary Statistics for Biomicroscopy Findings by Visit
- Incidence of Increased Severity by 2 or More Grades in Biomicroscopy Findings
- Listing of Subjects With Other Biomicroscopy Findings
- Listing of Subjects With Conjunctival Compression/Indentation or Chemosis
- Listing of Subjects With Increased Severity by 2 or More Grades in Biomicroscopy Findings
- Listings of Subjects with Infiltrates

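### The SAP takes the Pair 2 biomicroscopy baseline at Visit 3, after Pair 2 has been worn, so read literally the table and listing of increases of 2 or more grades cannot show any Pair 2 worsening

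*SAP*

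**What the plan says.** SAP 5.3 gives a general rule: "Baseline will be defined as the last measurement prior to exposure to study lenses". The next sentence gives a specific rule for slit lamp data: "For biomicroscopy data, baseline will be defined as Visit 1 for pair 1 and Visit 3 for pair 2".

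Protocol 12.6 defines the output that uses this baseline. Eyes are counted if a parameter rises by at least 2 grades "from baseline (last assessment prior to study lens exposure for each period) to any subsequent visit within the same period". SAP 5.3.2 lists the matching table, "Incidence of Increased Severity by 2 or More Grades in Biomicroscopy Findings", and a subject listing on the same criterion.

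The visit structure is the same in both documents. SAP Table 1-1 has "Visit 3: Follow-up Pair 2/Exit". Protocol section 10 says: "Study randomization will occur at Visit 1 with assigned lenses provided to take home at Visit 1 and Visit 2". Protocol 7.1 provides for three office visits. Protocol Table 3-1 schedules biomicroscopy at each of them, Visit 2 included.

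**The concern.** A baseline has to come before the exposure whose effect is measured. Pair 2 is worn between Visit 2 and Visit 3, so Visit 3 is the examination that shows what Pair 2 wear did. With Visit 3 as baseline, Period 2 has no later scheduled examination to compare with it.

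Biomicroscopy is one of three safety endpoints, and the increase of 2 or more grades is its only change-from-baseline output in the visible text. Each lens is Pair 2 in one of the two sequences, so both lenses lose their Period 2 data from this output. A zero produced by the rule would look the same as a true zero.

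**Working it through.** The documents state no figure to reproduce here: there is no sample size calculation, event rate or error rate. The check is of visit order first, then of scale.

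**1. Visit order**

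| Visit | Role (SAP Table 1-1; Protocol section 10) | Place in Period 2 |
|---|---|---|
| 1 | Screening, baseline, Pair 1 dispensed | Before |
| 2 | Pair 1 follow-up, Pair 2 dispensed | Last scheduled examination before Pair 2 wear |
| 3 | Pair 2 follow-up, exit | After about 14 or 28 days of Pair 2 wear |

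Protocol 12.6 works period by period, so its Pair 2 baseline is Visit 2. The SAP's general sentence does not mention periods. Read alone it could mean Visit 1 for both pairs, but it cannot mean Visit 3.

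**2. What the literal rule computes**

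Let V1, V2 and V3 be an eye's grades at the three visits.

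- SAP as written: Pair 2 change = V3 − V3 = 0 for every eye.
- Protocol 12.6: Pair 2 change = V3 − V2.

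On an assumed 0 to 4 scale there are 5 × 5 × 5 = 125 grade combinations. The pairs (V2, V3) with a rise of at least 2 number 3 + 2 + 1 = 6 (starting from grades 0, 1 and 2), and each occurs with 5 values of V1, giving 30. The literal rule flags 0 of these 30; a Visit 2 baseline flags all 30.

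**3. Unscheduled and early exit visits**

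These do not rescue the rule. An unscheduled examination during Pair 2 wear falls before Visit 3, so it is not subsequent to the stated baseline. A subject who leaves during Period 2 without reaching Visit 3 has no baseline.

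**4. Scale**

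The target is 32 completers (SAP Table 1-1), with both eyes fitted.

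- Eye-periods: 32 × 2 eyes × 2 periods = 128. Period 2: 32 × 2 = 64. Share: 64/128 = 50%, whatever the sequence split.
- If 36 subjects (the approximate enrolment) started Pair 1 and 32 finished Pair 2: 72 + 64 = 136, and 64/136 = 47%. This is an upper scenario for starters, since enrolment counts consented subjects and may include screen failures.

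Per lens, assume an even 16/16 sequence split and a common per-eye rate p in both periods. Each lens then has 64 eyes, 32 of them in Period 2.

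| | Visit 2 baseline | Visit 3 baseline, literal |
|---|---|---|
| Expected flagged eyes per lens | 64p | 32p |
| Percentage, Period 2 eyes kept in denominator | p | 32p/64 = p/2 |
| Percentage, Period 2 eyes dropped | not applicable | 32p/32 = p, on 32 eyes |

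The documents do not say which denominator would be used.

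For illustration, take the 64 Period 2 eyes of both lenses together. Assumed rates of 1%, 5% and 10% give 64 × 0.01 = 0.64, 64 × 0.05 = 3.2 and 64 × 0.10 = 6.4 expected flagged eyes with a Visit 2 baseline. The literal rule gives 0 each time.

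**The case against.** The strongest reply is that this is a one-digit slip with limited consequences. Protocol 12.6 states the intended rule, the SAP announces no departure from it, and a programmer who finds no post-baseline visit in Period 2 would probably notice. The study is a feasibility study with no safety hypotheses, inferential testing or success criterion. Pair 2 grades still appear in the by-visit summary. Infiltrates, compression or chemosis, and other findings have their own listings, and clinically relevant changes are reportable as adverse events under Protocol 11.2.

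The limits on the damage stand, and they confine the point to one table and one listing. The rest does not remove it. The visit-specific sentence is the more specific instruction in an approved SAP, and no visible text says that the protocol prevails. Code validated against the SAP would reproduce the error, and an undocumented workaround would depart from the plan. The by-visit summary is aggregate and adverse event reporting depends on the investigator's judgement, so neither replaces a within-eye comparison.

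Two narrower objections are fair. Only Protocol 12.6 leads directly to Visit 2; the SAP's general sentence merely rules out Visit 3. And the schedule does not say whether the Visit 2 examination comes before Pair 2 is inserted. That order is a reasonable inference, but the procedural detail is in the Manual of Procedures.

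**Conclusion.** The Pair 2 baseline in SAP 5.3 is wrong as written and must be corrected. It conflicts with Protocol 12.6, with the sentence before it and with the SAP's own visit table. Read literally, it makes the count of increases of 2 or more grades zero for Pair 2 whatever happens, across about half of all eye-periods: 64 of 128 with 32 completers.

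The loss of Period 2 events follows from the visit order alone and needs no assumed rate. The halving of the expected count per lens assumes an even sequence split and equal rates across periods. The halving of the percentage further assumes that Period 2 eyes stay in the denominator; otherwise the cost is precision, not bias.

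**What to change.** In SAP 5.3, name Visit 1 as the biomicroscopy baseline for Pair 1 and Visit 2, at the examination before Pair 2 is dispensed, as the baseline for Pair 2.

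Add a clause saying that exposure here means wear of the lens dispensed for that period. The reason is that both lenses are tried at Visit 1: Protocol section 10 says "Study contact lens fitting will occur at Visit 1 for both study lenses", and the visual acuity row of Table 3-1 lists "optimization and baseline measurements for both study lens types" at that visit. Once the visits are named, the clause is not essential for biomicroscopy, but it removes the ambiguity in the general sentence. Confirm in the Manual of Procedures that the Visit 2 slit lamp examination precedes insertion of Pair 2.

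The cost is one visit number, one clause and the matching derivation code. The Visit 2 examination is already scheduled, so no visit, procedure or data item is added.

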5.3.1 Adverse Events

The applicable definition of an AE is in the study protocol. All AEs occurring from when a participant signs informed consent to when a participant exits the study will be accounted for in the reporting.

Analysis and presentation of AEs will be separated into pre-treatment AEs, between-treatment AEs, and treatment-emergent AEs as defined below:

- Pre-treatment: an event that occurs after signing informed consent but prior to exposure to study products
- Between-treatment: an event that occurs one day after last exposure to period 1 (Pair 1) study lenses but prior exposure to period 2 (Pair 2) study lenses
- Treatment-emergent: an event that occurs from exposure to period 1 (Pair 1) study lenses until subject exits from the study, excluding those classified as between-treatment

The following tables and supportive listings will be provided:

- Incidence of All Ocular Treatment-Emergent Adverse Events
- Incidence of Ocular Serious Treatment Emergent Adverse Events
- Incidence of All Nonocular Treatment Emergent Adverse Events
- Incidence of Nonocular Serious Treatment Emergent Adverse Events

- Listing of All Ocular Treatment-Emergent Adverse Events
- Listing of All Nonocular Treatment-Emergent Adverse Events
- Listing of All Ocular Pre-Treatment Adverse Events
- Listing of All Nonocular Pre-Treatment Adverse Events
- Listing of All Ocular Between-Treatment Adverse Events
- Listing of All Nonocular Between-Treatment Adverse Events

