7 INVESTIGATIONAL PLAN

7.1 Study Design

[figure not shown]
This is a prospective, randomized, [REDACTED] bilateral crossover, controlled, subject-masked, daily wear clinical study to be conducted at a single site. Eligible habitual soft contact lens wearers will be randomized to 1 of the 2 crossover sequences. Subjects will be masked. A designated study staff member will prepare the contact lenses for dispensing.

Subjects will be expected to participate in a pre-screening and attend 3 office visits: Screen/Baseline/Dispense Lens Pair 1, Follow-up Lens Pair 1/Dispense Lens Pair 2, Follow-up Lens Pair 2/Exit. AOHP will be worn for ~14 days and TOTAL30 will be worn for ~28 days. The total expected duration of participation for each subject is approximately 1.5 months. Subjects will be randomized to wear the assigned product sequence in both eyes, either the test TOTAL30 contact lenses as Pair 1, followed by the comparator AOHP contact lenses as Pair 2, or vice versa. All study contact lenses will be prescribed according to subject's prescription and can be optimized per study lens type, however test and comparator lenses should be dispensed within ± 0.25 D of each other.

Subjects will be expected to wear their study contact lens in a daily wear modality for at least 5 days per week 8 hours a day, over a 14 day (AOHP) or 28 day period (TOTAL30). AOSEPT PLUS with HydraGlyde Cleaning & Disinfecting Solution will be used for daily cleaning and disinfection.

On the day of Visits 2 and 3, subjects will be asked to wear the study lenses at least 6 hours and prior to their study visit. Follow-up visit time to be within ± 2 hours of baseline visit time.

[REDACTED]
[REDACTED]

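### Does the SAP's separate class for adverse events between Pair 1 and Pair 2 distort the per-lens adverse event tables?

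*SAP*

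**What the plan says.** SAP 5.3.1 sorts adverse events into three classes. Pre-treatment events fall after consent and before any study lens. A between-treatment event is "an event that occurs one day after last exposure to period 1 (Pair 1) study lenses but prior exposure to period 2", that is, before the second pair is worn. A treatment-emergent event is "an event that occurs from exposure to period 1 (Pair 1) study lenses until subject exits from the study, excluding those classified as between-treatment".

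The outputs differ by class. Treatment-emergent events get four incidence tables (ocular and nonocular, all and serious) plus listings. Pre-treatment and between-treatment events get ocular and nonocular listings only.

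Two other places bear on this. SAP 2.1 mentions listings for one group: "Adverse events occurring from the time of informed consent but prior to first exposure to the study product will be summarized in subject listings". Protocol 12.6 describes treatment-emergent reporting and a listing of events before exposure, and does not mention a between-treatment class.

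**The concern.** Three features make the rule look faulty.

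- **It is one-sided.** An event two days after the last Pair 1 wear is only listed if Pair 2 has not yet been worn. The same event two days after the last Pair 2 wear is tabulated if the subject has not yet exited. The serious-event tables are affected in the same way.
- **It is not a general off-lens rule.** Subjects are asked to "wear their study contact lens in a daily wear modality for at least 5 days per week 8 hours a day", so each period contains days without lenses, and events on those days count. For device deficiencies two classes suffice: "Two listings for device deficiencies, prior to exposure of study contact lenses and treatment-emergent, will be provided".
- **The upper bound is undefined for some subjects.** A subject who stops in Period 1 has no Pair 2 exposure. One programmer could tabulate a late event as treatment-emergent and another could send it to the between-treatment listing.

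Describing safety is the stated safety objective (Protocol Table 6–3). If events were missed in this way, incidence would be understated for whichever lens came first. With 32 to 36 subjects, one subject moves a percentage visibly.

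**Working it through.** The plan gives no figure to reproduce. The check is to apply the definitions to cases and then bound the excluded time.

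**Inputs.** About 36 enrolled and 32 completers (Protocol 3); 28 days of TOTAL30 and 14 of AOHP (SAP Table 1–1); wear on at least 5 days in 7 (Protocol 7.1); Pair 2 dispensed at Visit 2 and exit at Visit 3, with no washout described (Protocol 10). For visit days, the footnote to Protocol Table 3–1 says: "Subjects are required to wear the study lenses at least 6 hrs on the day of follow-up visits prior to the visit".

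**Step 1: the rule applied to cases.** Suppose Pair 1 is last worn on day 14.

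| Case | Class | Output |
|---|---|---|
| Onset day 14 | Treatment-emergent | Table and listing |
| Onset day 15, Pair 2 first worn day 16 | Between-treatment | Listing only |
| Onset day 43, Pair 2 last worn day 42, exit day 44 | Treatment-emergent | Table and listing |
| Onset day 15, Pair 2 never worn, exit day 20; bound needs an actual Pair 2 wear | Treatment-emergent | Table and listing |
| Same case; bound read as open | Between-treatment | Listing only |

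The asymmetry and the two readings are both confirmed.

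**Step 2: length of the window on schedule.** If Pair 2 is first worn g days after the last Pair 1 wear, the between-treatment class covers max(0, g − 1) whole days. For g = 0, 1, 2, 3 this gives 0, 0, 1, 2 days. Pair 1 is worn on the day of Visit 2 and Pair 2 is handed over then, so g = 0 or 1 is the ordinary case. After Pair 2 the corresponding time is about 0 days, because Visit 3 is also the exit.

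**Step 3: an extreme bound.** Assume all 36 are randomized 18:18, all complete, and every subject takes both weekly non-wear days (7 − 5 = 2) straight after Visit 2.

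- Excluded time per lens: 18 × 2 = 36 subject-days.
- Planned time: 36 × 28 = 1008 (TOTAL30) and 36 × 14 = 504 (AOHP).
- Shares: 36/1008 = 3.6% and 36/504 = 7.1%.

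Nothing in the documents suggests that subjects would behave this way, so these are ceilings and not a likely impact. For scale, off-lens days already counted inside a period run up to 28 × 2/7 = 8 (TOTAL30) and 14 × 2/7 = 4 (AOHP) per subject.

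**Step 4: subjects who leave early.** The plan allows for 36 − 32 = 4 non-completers (4/36 = 11.1%). That number also has to cover screen failures and those who stop during Pair 2, so planned Period 1 stops are some part of 4. The ambiguity bites only if such a subject also has a new event that starts a day or more after the last wear and before exit. One such subject would move a lens's incidence by 1/36 = 2.8 to 1/32 = 3.1 percentage points, as any single reclassification would.

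**Step 5: direction.** The gap follows TOTAL30 in one sequence and AOHP in the other. With 1:1 allocation and equal post-wear event rates, the expected loss is the same for both lenses and the difference between them is not biased.

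**The case for a change.** The best case for a change is that the fix is cheap and the plan gives no reason for the asymmetry. Each event could be attributed to the last dispensed lens worn, from first dispensed wear of Pair 1 until exit, with a between-treatment flag kept in the listing. That would treat both pairs alike, follow the simpler scheme in Protocol 12.6, and remove any choice for subjects without Pair 2. A serious event outside the serious-event table is also unattractive in principle.

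Part of this stands: the asymmetry is in the text, and one clarifying clause is absent. The rest is weaker.

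- Non-wear days within a period lie between two wears of the same lens, so attribution is clear. The gap at the crossover lies between two different lenses, and giving it its own class is a recognised, prespecified choice.
- A device deficiency belongs to an identifiable lens whatever its date, so two classes there set no precedent for adverse events.
- SAP 2.1 says that pre-exposure events are listed. It does not say that no other events may be handled by listing.
- The alternative has its own cost: it charges off-lens, possibly unrelated events to the Pair 1 lens.
- Serious events are not hidden. SAP 5.3.1 accounts for every event up to exit, and Protocol 12.6 also has serious events and those leading to discontinuation identified.

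A side issue is the fitting visit, since "Study contact lens fitting will occur at Visit 1 for both study lenses". An event during fitting could raise the question of which lens counts as exposure. The analysis-set sentence in SAP 2.1 is partly blacked out, so this cannot be judged and is not counted as missing.

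**Conclusion.** No change is needed. The between-treatment class is a fair trade-off: it keeps events that belong clearly to neither lens out of the per-lens tables, at the price of a small asymmetry with the end of Period 2. The wording for subjects who never wear Pair 2 is a gap that analysts fill sensibly. The definitions class events, and treatment-emergent is the residual class, running "until subject exits from the study, excluding those classified as between-treatment". Between-treatment presupposes a second treatment, so without Pair 2 the event stays treatment-emergent for the Pair 1 lens.

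The excluded window is 0 whole days when the switch is made the same or next day, and 2 days at the weekly wear minimum. A longer window requires a subject to stop Pair 1 before Visit 2, remain in the study, wear Pair 2 later, and have a new event in between. No event is lost from the report.

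This rests on subjects following the visit schedule, on events that prompt lens removal starting during wear or on the same day, and on similar post-wear event rates for the two lenses. The documents give no event or early-stopping rates, so the effect is judged to be about nil and is not estimated. With no hypotheses and no inferential testing, no study conclusion turns on it.
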